TMU-Joint Institutional Review Board

Title:

Transcranial Electrical Stimulation with Special Waveform for
Upper Extremity Rehabilitation for Patients with Stroke

Approval Number: N201702070

Date: 2020/01/31

Study Protocol and Statistical Analysis Plan

➤ Participants

The present study is a single-blinded, randomized controlled trial pilot study performed at Taipei Medical University Hospital in Taiwan. Experiments is conducted under a protocol approved by the Joint Institutional Review Board of Taipei Medical University with registration number (N201702070). All experiments in this research are performed in accordance with the relevant guidelines and regulations at Taipei Medical University.

Potential participants are identified from Taipei Medical University Hospital. participants (n= 24) are eligible according to the following criteria and consented to take part. The flowchart for the inclusion of patients is as below text. We include patients with ischemic or hemorrhagic chronic stroke diagnosed by the neurologist and meeting the following inclusion criteria: (1)aged ≥ 20 years; (2) unilateral cerebral stroke with hemiplegia and Brunnstrom stage IV-V;(3) adequate understanding of verbal/written information and physically able to complete the motor learning of functional tasks with the affected hand. Exclusion criteria are as follows: (1) upper motor neuron impairment (2) autonomic nervous system is not stable (3) extremely sensitive to electrical stimulation and cannot tolerate it (4) contractures in the upper extremity or limitation of joint motion (5) severe spasticity (6) myositis ossificans (7) a history of arrhythmia (8) medical electronic device implants, such as a pacemaker (9) decubitus or scalp wounds (10) metal head or neck implants (11) severe cognitive dysfunction or active psychiatric diseases, such as schizophrenia or dissociative identity disorder (12) a history of seizure or organic brain disease (13) severe traumatic brain injury (14) drug or alcohol abuse (15) malignant tumor or autoimmune rheumatic disease, such as systemic lupus erythematosus, rheumatoid arthritis, or ankylosing spondylitis .

➤ Experimental Protocol and Design

Participants were randomly assigned to a conventional rehabilitation (CR) combined with real-tDCS+iTBS (experimental group) or sham-CR (control group) using a computer-generated randomized scheme. Randomization, functional outcome measurements, and data analysis were performed by trained research staffs who were not involved in the intervention. All participants received the similarly conventional rehabilitation therapy and duration of real/sham-tDCS+iTBS stimulation in both groups. Conventional rehabilitation treatments (includes fine motor skill training, normal limb posture, active range of motion exercises, muscle strengthening exercises) were conducted by certified occupational therapists who were blinded to the group assignment and trained according to

the investigator's protocol. This experimental protocol consisted of 18 sessions, a 20-min stimulation program per session during the 1 hour conventional rehabilitation program per session activity, 3 days per week for 6 weeks.

➤ **Outcome Measures.**

A. Experimental Protocol and Design

Participants were randomly assigned to a conventional rehabilitation (CR) combined with real-tDCS+iTBS (experimental group) or sham-CR (control group) using a computer-generated randomized scheme. Randomization, functional outcome measurements, and data analysis were performed by trained research staffs who were not involved in the intervention. All participants received the similarly conventional rehabilitation therapy and duration of real/sham-tDCS+iTBS stimulation in both groups. Conventional rehabilitation treatments (includes fine motor skill training, normal limb posture, active range of motion exercises, muscle strengthening exercises) were conducted by certified occupational therapists who were blinded to the group assignment and trained according to the investigator's protocol. This experimental protocol consisted of 18 sessions, a 20-min stimulation program per session during the 1 hour conventional rehabilitation program per session activity, 3 days per week for 6 weeks.

B. Fugl-Meyer Assessment-Upper Extremity (FMA-UE)

At the week before treatment initiation (baseline), clinical and demographic characteristics for each patient were collected. For all groups, the functional outcomes were measured at the baseline, immediately, and 6 weeks after 18 therapeutic sessions (post-treatment) by a researcher blinded to which subjects are receiving the real treatment. The primary outcome of the study was the Fugl-Meyer Assessment-Upper Extremity (FMA-UE). The FMA-UE was performed (score ranges from 0 to 66) to assess upper limb motor recovery. This test has been considered as core measures to detect changes in motor recovery in stroke and rehabilitation trial. [Hsieh, 2009]. The each tasks is rated from 0 to 2, with a higher score representing better hand function performance of stroke patients.

C. Jebson-Taylor Hand Function Test (JTT)

The JTT of hand function is a widely used to assess a broad range of functional hand motor skills that reflects activities of daily living. JTT has shown to be a reliable, valid, and normative data are available at all ages and both genders. We included in our analyses seven subtests of the JTT: writing, turning cards, picking up small objects, picking up beans

with a tea spoon, stacking checkers, lifting light cans and lifting heavy cans. Participants were instructed to perform task as fast and accurately as possible. Total JTT time and subtest JTT times (maximum measure time is 45 sec for each subset) were recorded for analysis.

D. Finger-to-Nose Test (FNT)

The FNT is often used to assess upper-limb coordination after stroke. While the patients sat on the chair with the examiner in front of them, they were asked to alternately touch their nose and then extend their finger to touch the examiner's finger as quickly as possible. The numbers of touch events within 1 minute were recorded for analysis.

➤ **Statistical Analysis**

Normality will be assessed using Kolmogorov–Smirnov tests and most of the outcome measures are not normally distributed. Therefore, nonparametric statistical analyses are used to assess the data. Baseline demographic and clinical measures (mean, standard deviation, and median) are compared between two groups using the Mann–Whitney U-test for continuous variables or Pearson's chi-squared test for categorical variables. The primary and secondary outcome measures are analyzed by Wilcoxon matched-pairs signed-ranks test to investigate time effects (baseline and post-treatment) within groups. Mann-Whitney rank sum test is used to test differences in outcomes among groups. Change in subsets JTT times after stimulation in percentage are calculated according to the following equations: Change in % = (Baseline/Post-treatment *100–100). Statistically significant differences are considered at $p < 0.05$. Statistical analysis is performed using SigmaPlot, version 10.0 (Systat Software, Inc., USA).

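### The between-arm comparison of FMA-UE is not named as the primary efficacy test and has no stated visit or scale

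*Combined protocol and SAP*

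**What the plan says.** The Participants section describes the trial thus: "The present study is a single-blinded, randomized controlled trial pilot study", with 24 participants. The FMA-UE paragraph under Outcome Measures names FMA-UE (0 to 66) as the primary outcome, by instrument only. On timing it says "the functional outcomes were measured at the baseline, immediately, and 6 weeks after 18 therapeutic sessions (post-treatment"; the bracketed word follows a phrase that covers two later visits.

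The Statistical Analysis section then gives two sentences on testing outcomes:

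- Within arms: "The primary and secondary outcome measures are analyzed by Wilcoxon matched-pairs signed-ranks test to investigate time effects (baseline and post-treatment) within groups".
- Between arms: "Mann-Whitney rank sum test is used to test differences in outcomes among groups".

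The first mentions the primary outcome. The second names no outcome, no time point, and neither change nor post-treatment score. The only change measure defined is a percentage change for the JTT subtests. One threshold, p < 0.05, covers every test. No sentence ranks the tests or names a primary comparison.

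On treatment, Experimental Protocol and Design says: "All participants received the similarly conventional rehabilitation therapy and duration of real/sham-tDCS+iTBS stimulation in both groups".

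**The concern.** Both arms receive rehabilitation, so a before/after gain in either arm mixes the effect of rehabilitation, practice and time with any effect of stimulation. The sham control removes these only through the between-arm contrast. That contrast should therefore be the most tightly specified item in the plan, yet it is the least specified.

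Two things are at stake. First, with the visit and possibly the scale open, several between-arm FMA-UE tests fit the text equally well, each at 0.05, and the most favourable could be reported as the result. Second, if the sentence is read as a comparison of raw post-treatment scores, the baseline FMA-UE that every participant supplies is not used, which can cost much of the power of a 24-person trial. A lesser risk is that a significant within-arm result for the primary outcome, standing beside an unranked between-arm test, is misread as evidence for stimulation. In a pilot the practical harm is an unsupported or missed signal carried into a later trial.

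**Working it through.** **Inputs from the documents.** 24 participants (Participants); threshold 0.05 (Statistical Analysis); baseline plus two later assessments (Outcome Measures, FMA-UE).

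**Assumptions, because the documents are silent.** 1:1 allocation (12 per arm), two-sided tests, normal data, and the effect size and correlations shown below. The plan gives no power or error calculation and no derivation of 24, so there is no figure of its own to reproduce.

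**1. Tests that fit the wording.** 2 visits × 2 scales (post-treatment score, change from baseline) = 4 between-arm tests of FMA-UE.

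**2. One prespecified test.** For 12 v 12 the exact Mann-Whitney test rejects when the smaller U is at most 37. The two-sided level is 0.0449, so 0.0449 / 2 = 0.022 in favour of real stimulation.

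**3. Several unranked tests, no stimulation effect.** If the tests were independent, the chance of at least one rejection would be 1 − 0.95² = 9.75% for two and 1 − 0.95⁴ = 18.5% for four. They are correlated, so the simulated figures (at least 20,000 trials per scenario) are lower. With baseline-to-later correlation b and correlation l between the later visits, the two change scores correlate at (1 − 2b + l) / (2(1 − b)). When b = l this is 0.5 whatever the value. With b = 0.7 and l = 0.9 it is 0.5 / 0.6 = 0.83. Both patterns are therefore shown; *more alike* means roughly b = 0.7 with l = 0.9, up to b = 0.9 with l = 0.97.

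| Choice left open | Correlations | Favours real | Two-sided |
|---|---|---|---|
| None (one test) | any | 2.2% | 4.5% |
| Either visit, on change | all equal, 0.5-0.9 | 4.0-4.2% | about 8% |
| Either visit, on change | later visits more alike | 3.4-3.6% | about 7% |
| Either visit, on post score | all equal, 0.5-0.9 | about half of next column | 6.8-8.2% |
| Any of four | all equal, 0.5-0.9 | 7.0-7.7% | 14-15% |
| Any of four | later visits more alike | 6.1-6.3% | about 12% |

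The one-direction column is to be compared with 2.2%, and the two-sided column with 4.5%.

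**4. What the scale does to power.** Take an assumed effect of 0.8 SD of the score, and correlation r between baseline and the chosen visit. In SD units of the score, the spread is 1 for the post score, √(2(1 − r)) for change and √(1 − r²) after baseline adjustment. Dividing 0.8 by these gives the effective standardized effect; power is from simulation with 12 per arm.

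| r | Post score | Change | Baseline-adjusted |
|---|---|---|---|
| 0.5 | 0.80; 43% | 0.8/1.00 = 0.80; 43% | 0.8/0.866 = 0.92; about 54% |
| 0.7 | 0.80; 43% | 0.8/0.775 = 1.03; 64% | 0.8/0.714 = 1.12; about 71% |
| 0.9 | 0.80; 43% | 0.8/0.447 = 1.79; 98% | 0.8/0.436 = 1.83; about 98% |

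Change alone gains nothing at r = 0.5 and loses below it. Adjustment is at least as good throughout this range.

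**The case against.** The strongest reply is that the two sentences carry labels: the Wilcoxon tests look at time effects and the Mann-Whitney test at differences between groups, so the treatment comparison is already identified. That largely stands. A reader might infer that the plan will judge efficacy from before/after tests. Such a reader could point out that, with no stimulation effect, the real-arm Wilcoxon test is significant for improvement in about 22%, 67% and 85% of trials when both arms gain 0.4, 0.8 and 1.0 SD of change. The documents do not support that reading. Those percentages are the power to detect a before/after gain that truly exists; at no gain the figure is 2%. The pattern of real significant and sham not, which reaches at most 25%, matters only under a decision rule that the plan does not contain. What remains is a risk of misreading.

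Second, the scale may be less open than the visit. FMA-UE is defined as a score, and change is mentioned only for the JTT, so the post-treatment score is the plainest reading. That is fair, and it weakens the four-choice figure. It leaves the visit open, however, and it is the reading that leaves the baseline unused.

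Third, this is a pilot that makes no confirmatory claim and no promise of error control. That lowers the severity. The plan nevertheless names a primary outcome and a significance threshold.

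Fourth, it may be too late. Design and outcomes are written largely in the past tense, and the analysis section already states that "most of the outcome measures are not normally distributed". The documents do not settle whether unblinded data had been seen.

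**Conclusion.** The point holds as a gap in specification. The primary between-arm comparison cannot be reproduced from the plan, because its visit is not stated, its scale is at best implied, and it is not ranked above the other tests. Leaving the visit open raises the two-sided error from 4.5% to about 7-8%. If the scale is open too, the figure is about 12-15%. In favour of real stimulation, the corresponding rates are 2.2%, about 3.4-4.2% on change, and about 6-8%. These figures rest on 12 per arm, normal data and assumed correlations; they show what the wording permits, and a reader should not infer that the trial did or will select among tests. Using the score alone can also forgo substantial power, depending on a baseline correlation that the documents do not give. The plan does not treat within-arm significance as efficacy, and it should not be criticised as if it did. For a pilot this should be fixed, at the low end of that grade.

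**What to change.** In the Statistical Analysis section:

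- Name one between-arm comparison of FMA-UE as the primary efficacy comparison of the pilot, either baseline-adjusted or a Mann-Whitney test on change from baseline.
- Tie it to one visit, and define *post-treatment* as that visit.
- Label the other visit and all within-arm Wilcoxon tests descriptive.
- If unblinded data have already been seen, say so and label the choice post hoc.

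With one Mann-Whitney test the two-sided error at 12 v 12 is 0.0449. Naming the post-treatment score at one visit would also close the ambiguity, but would leave the baseline unused.

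The cost is wording only: no new data or visits. The downside is that results at the other visit and within-arm significance can no longer support an efficacy claim. If the baseline correlation may be 0.5 or less, change brings no gain over the post score, which favours the adjusted comparison. If the choice has to be post hoc, the label informs the reader but does not restore error control.

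### The primary between-group test leaves open post score or change and which visit, and it makes no use of the baseline FMA-UE already collected

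*Combined protocol and SAP*

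**What the plan says.** The study is a "single-blinded, randomized controlled trial pilot study" of 24 patients in two arms. The FMA-UE section under Outcome Measures makes FMA-UE (0 to 66) the primary outcome and sets the timing: "the functional outcomes were measured at the baseline, immediately, and 6 weeks after 18 therapeutic sessions (post-treatment". On the natural reading that is a baseline and two later assessments.

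Statistical Analysis then contains:

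- **Between arms:** "Mann-Whitney rank sum test is used to test differences in outcomes among groups". No visit, scale or covariate is given.
- **Within arms:** outcomes are "analyzed by Wilcoxon matched-pairs signed-ranks test to investigate time effects (baseline and post-treatment) within groups".
- **Baseline:** measures are compared between arms by significance test, with no stated consequence.
- **Change:** a formula is given for JTT subtests only: "Change in subsets JTT times after stimulation in percentage are calculated according to the following equations". FMA-UE has none.
- **Choice of method:** nonparametric tests are chosen because "most of the outcome measures are not normally distributed", although the normality test is described in the future tense.

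**The concern.** The sentence that should define the primary comparison does not identify one test. Post score or change, at either of two visits, gives four candidates, and these can reach different conclusions on the same data.

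Neither scale deals fully with a chance difference at baseline. The post-score test carries the imbalance into the result when baseline and post scores are strongly correlated. The change-score test over-corrects when they are weakly correlated. The within-arm Wilcoxon tests do not compare arms, and the baseline significance tests adjust nothing. With 24 patients, chance imbalance and lost precision both matter. Non-normality does not rule out adjustment, because rank-based ANCOVA exists.

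**Working it through.** **Inputs from the document.** Total n = 24; two arms; FMA-UE primary; significance at p < 0.05. There is no power, effect size, SD or correlation to reproduce.

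**Assumptions.** 12 per arm, two-sided test, true effect 0.8 SD, and baseline-to-post correlation r from 0.3 to 0.9.

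**Step 1: precision by formula (normal approximation).** In units of the post-score SD, the relevant SD is 1 for the post score, √(2(1−r)) for change and √(1−r²) for ANCOVA. The detectable difference at 80% power is (1.96 + 0.84) × √(2/12) × SD.

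- Post score: 2.80 × 0.408 = 1.14 SD at any r.
- r = 0.3: change 1.35, ANCOVA 1.09.
- r = 0.5: change 1.14, ANCOVA 0.99.
- r = 0.8: change 0.72, ANCOVA 0.69.

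Change is therefore worse than the post score below r = 0.5 and better above it. ANCOVA is at least as precise as either throughout.

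**Step 2: power by simulation** (exact Mann-Whitney, normal data, 20,000 trials per cell, effect 0.8 SD), in percent:

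| r | Post score | Change | ANCOVA | Quade |
|---|---|---|---|---|
| 0.3 | 42–43 | 32 | 48 | 46 |
| 0.6 | 42–43 | 51 | 63 | 58 |
| 0.7 | 42–43 | 64 | 73 | 66 |
| 0.8 | 42–43 | 81 | 86 | 79 |
| 0.9 | 42–43 | 98 | 99 | 95 |

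ANCOVA gains about 6 to 56 points over the post-score test. Over the change test it gains 16 points at r = 0.3 (48 − 32), about 12 at 0.6, 9 at 0.7, 5 at 0.8 and 1 at 0.9. Quade is slightly below the change test at r = 0.8 and 0.9.

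The pattern survives less tidy data. With integer FMA-UE clipped to 0–66 (assumed baseline mean 48, SD 10, control gain 3), power is 42–43% for post, 28–91% for change, 47–97% for ANCOVA and 46–95% for Quade. With a JTT total built from seven subtests capped at 45 s (assumed median 20 s), it is 40–42%, 27–84%, 45–91% and 45–88%.

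**Step 3: does the open choice matter?** With the 0.8 SD effect, the post-score and change tests disagree on significance in 31–56% of trials. With no effect, each single test rejects about 4–5%. If the more favourable result were taken, the rate is 8–9% for post versus change at one visit. It is 11–15% for both scales over two visits (visit-to-visit correlation 0.70–0.95 assumed).

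**Step 4: chance baseline imbalance.** The probability of a baseline difference above 0.5 SD is 2 × (1 − Φ(0.5/√(2/12))) = 2 × (1 − Φ(1.22)) = 0.22. With no treatment effect, a baseline difference D produces an expected difference of rD in post scores and (r − 1)D in change. For D = 0.5 this is 0.40 and −0.10 SD at r = 0.8, and 0.15 and −0.35 SD at r = 0.3. ANCOVA removes it.

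In simulated null trials with imbalance above 0.5 SD:

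- the post-score test rejects 11–19% at r = 0.6–0.9 (6% at 0.3);
- the change test rejects 5–8% at r = 0.6–0.9 (11% at 0.3);
- ANCOVA rejects about 5%.

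The planned baseline Mann-Whitney test detects only about 20% of those imbalances.

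**The case against.** The best defence is that an unadjusted Mann-Whitney test is legitimate in a small pilot that makes no power claim. Randomization holds the error of any single fixed test at 5% or below, and the raised conditional rejection rates are offset in the better-balanced trials. This stands: the planned test is not invalid.

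It can also be said that post-treatment is used as one time point in the Wilcoxon sentence and the JTT formula, so a single visit may be intended. That softens the visit ambiguity but does not remove it. The label does not separate the immediate from the 6-week assessment, and the Mann-Whitney sentence names neither.

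Third, the gains rest on assumed inputs. If change was intended and r is high, ANCOVA adds little and Quade adds nothing. Naming Mann-Whitney on change at one visit would already close the definitional gap. This also stands, but that smaller fix over-corrects if r turns out low, and r is not known in advance.

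Finally, the 8–9% and 11–15% rates assume that the most favourable result is picked. Nothing in the document suggests this, so they are upper scenarios. Under the null, the two scales disagree in only 7–8% of trials.

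**Conclusion.** The concern holds. That the primary between-group test is undefined as to scale and visit follows from the text and depends on no assumed number. The absence of baseline adjustment is a loss of precision and leaves chance imbalance uncorrected; it is not an error in the test's overall validity. Its size cannot be fixed from the document. With 12 per arm and a 0.8 SD effect, it ranges from about 1 point of power (change tested, r = 0.9) to 56 points (post score tested, r = 0.9). The baseline score is already collected, so the improvement is nearly free and should be made before the data are analysed.

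**What to change.** State the primary analysis as ANCOVA of FMA-UE at one named post-treatment visit, on group and baseline FMA-UE, with the adjusted difference and its confidence interval. Make the other visit secondary. Do not let the method depend on a normality test. If a nonparametric analysis is wanted, name Quade's rank ANCOVA in advance instead.

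Use a baseline-adjusted analysis for FNT and total JTT time as well. The rank version is preferable for JTT because of the ceiling: "maximum measure time is 45 sec for each subset". Do not use baseline p-values to judge imbalance.

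The cost is SAP wording and one model. ANCOVA spends one degree of freedom and assumes a linear baseline-to-post relation. On normal data Quade gives up about 2–8 points of power to ANCOVA at 0.8 SD, and about 13 points at 0.5 SD with r = 0.9 (75% against 62%). On the simulated capped JTT total the loss is at most about 3 points.
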